6.1.1. Induction Phase

All eligible subjects will self-administer the intranasal study drug twice a week for 4 weeks at treatment sessions at the study site. Intranasal treatment sessions should not take place on consecutive days.

The esketamine nasal spray dose titration in the Induction Phase for subjects <65 years of age is described in [Table 2](#):

Table 2: Induction Phase Dose Titration of Esketamine Nasal Spray, Subjects <65 Years

Day	Dose	Dose Titration Guidance
Day 1	56 mg	
Day 4	56 or 84 mg	The dose may remain at 56 mg or be increased to 84 mg, as determined by the investigator based on efficacy and tolerability.
Day 8, 11, 15, 18, 22, 25	56 or 84 mg	The dose may be increased to 84 mg (if previous dose was 56 mg), remain the same, or be reduced to 56 mg (if previous dose was 84 mg), as determined by the investigator based on efficacy and tolerability.

The esketamine nasal spray dose titration in the Induction Phase for subjects ≥ 65 years of age is described in [Table 3](#):

Table 3: Induction Phase Dose Titration of Esketamine Nasal Spray, Subjects ≥ 65 Years

Day	Dose	Dose Titration Guidance*
Day 1	28 mg	
Day 4	28 or 56 mg	The dose may remain at 28mg or be increased to 56mg, as determined by the investigator based on efficacy and tolerability.
Day 8, 11, 15, 18, 22, 25	28, 56 or 84 mg	The dose may remain the same, or be increased or reduced by 28mg from the previous dosing session, as determined by the investigator based on efficacy and tolerability.

6.1.2. Optimization/Maintenance Phase

Subjects will self-administer the intranasal study drug at treatment sessions at the study site. Intranasal treatment sessions should not take place on consecutive days.

For the first 4 weeks of the optimization/maintenance phase (Week 1 to Week 4):

- Subjects from the induction phase of study 54135419TRD3008, who enter the optimization/maintenance phase will continue on the same dose of esketamine nasal spray from the induction phase and have a weekly intranasal treatment session frequency (ie, reduced frequency from the twice-weekly frequency in the induction phase).
- Subjects who were responders at the end of the induction phase of ESKETINTRD3001, ESKETINTRD3002 or ESKETINTRD3006 (US sites only) who enter the optimization/maintenance phase will have a weekly intranasal treatment session frequency (ie, reduced frequency from the twice-weekly frequency in the induction phase). However, as the ESKETINTRD3001, 3002 and 3006 intranasal study medication is blinded at the time of entry into the current study, subjects entering the optimization/maintenance phase should start at 56 mg. The dose may remain at 56 mg or be increased to 84 mg, as determined by the investigator based on efficacy and tolerability.
- With sponsor approval, subjects from ESKETINTRD3003 and ESKETINTRD3004 entering directly from the induction phase, who were determined to not meet the criteria for response in those studies may enter the optimization/maintenance phase of 54135419TRD3008 and will have a weekly intranasal treatment session frequency from week 1 to week 4 (ie, reduced frequency from the twice-weekly frequency in the induction phase). In addition, a one-time dose change will be allowed at study entry.

- With sponsor approval subjects from ESKETINTRD3006 (US sites only) entering directly from induction phase and determined to not meet criteria for response in that study may enter the optimization/maintenance phase. However, as the ESKETINTRD3006 intranasal study medication is blinded at the time of entry into the current study, subjects entering the optimization/maintenance phase from study ESKETINTRD3006 will start at 56 mg. The dose may remain at 56 mg or be increased to 84 mg, as determined by the investigator based on efficacy and tolerability. Subjects will have a weekly intranasal treatment session frequency from week 1 to week 4 (ie, reduced frequency from the twice-weekly frequency in the induction phase).
- Subjects entering the optimization/maintenance phase from study ESKETINTRD3005 will also have a weekly intranasal treatment session frequency. However, as the ESKETINTRD3005 intranasal study medication is blinded at the time of entry into the current study, the dose of esketamine nasal spray will be administered as outlined in [Table 4](#).

Table 4: Optimization/Maintenance Phase Week 1 to 4: Dose Titration of Esketamine Nasal Spray for Responder Subjects Entering from ESKETINTRD3005

Week	Dose	Dose Titration Guidance
Week 1	28 mg	
Week 2	28 or 56 mg	The dose may remain at 28mg or be increased to 56mg, as determined by the investigator based on efficacy and tolerability
Week 3 and 4	28, 56 or 84 mg	The dose may remain the same or be increased or reduced by 28mg from the previous dosing session, as determined by the investigator based on efficacy and tolerability. For those who have had a prior down titration from a higher dose, a dose increase by 28 mg is allowed based on clinical judgment.

- Subjects entering the optimization/maintenance phase from study ESKETINTRD3003 (Direct Entry) or ESKETINTRD3004 who were ongoing in the Optimization, Maintenance, or Optimization/Maintenance phase, respectively, will have the option to have their current intranasal dosing frequency adjusted at the time of entry into 54135419TRD3008 study and should remain on the selected frequency from week 1 to week 4 (inclusive). A one-time dose change will be permitted at study entry.
- Subjects entering the optimization/maintenance phase from study ESKETINTRD3003 (Transferred Entry) will start at 56 mg. The dose may remain at 56 mg or be increased to 84 mg, as determined by the investigator based on efficacy and tolerability. In addition, subjects will have the option to have their current intranasal dosing frequency adjusted at the time of entry into 54135419TRD3008 study and should remain on the selected frequency from week 1 to week 4 (inclusive).

After Week 4 (ie, starting at Week 5), based on the investigator's clinical judgment, the dose of esketamine for all subjects can be adjusted based upon efficacy and tolerability.

Starting at Week 4, the frequency for subsequent intranasal treatment sessions will be adjusted (if applicable) based on the algorithm outlined in [Table 5](#) at fixed, 2-week intervals.

Table 5: Algorithm for Adjusting Intranasal Treatment Session Frequency (if applicable) Starting Week 4

Current treatment session frequency	CGI-S score at current visit ^a	
	≤ 3	>3
Weekly	Change to every other week frequency	No change in frequency
Every other week	No change in frequency or change to every 4 weeks per clinical judgment	Change to weekly frequency
Every 4 weeks	No change in frequency	Change to weekly or every other week frequency per clinical judgment

^a Note: The CGI-S is administered every 2 weeks from Week 4 through the end of the Optimization/Maintenance Phase, adjustment of the intranasal treatment session frequency is only permitted at the fixed, 2-week interval (based on CGI-S performed at that visit), and every 4 weeks for subjects dosed at the 4 week interval.

For example, if at Week 4 a subject is currently at a weekly treatment session frequency and the CGI-S score at Week 4 is a 2, the intranasal treatment session frequency will be changed from weekly to every other week (ie, the next treatment session for this subject will be at Week 6).

Missed Doses

If a subject missed a dose/s and the depression symptoms worsened, the investigator can go back to more frequent dosing if clinically applicable until the subject is stable.

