3.2.4. Intranasal Treatment Group and Dose Selection

Induction Phase

All subjects will receive open-label esketamine nasal spray during this phase.

The 56 mg and 84 mg doses and administration interval (2 treatment sessions per week for 4 weeks) for this phase were based on the sponsor's previous clinical data, in particular the results from Studies ESKETIVTRD2001, KETIVTRD2002, ESKETINTRD1001, and Panel A of Study ESKETINTRD2003, described above in Section 1.1.2, and is aligned with the induction phase of the prior study the subject is coming from.

The data from Study ESKETINTRD2003 Panel A support the hypotheses that both the 56 mg and 84 mg doses are effective as a treatment for depression in subjects with TRD; that they have a rapid onset of effect; and that 2 treatment sessions per week can sustain the response throughout the 4-week duration of the induction phase. In addition, the 56-mg and 84 mg dosages were generally well tolerated by subjects.

To potentially improve tolerability, for those subjects that become ≥ 65 years of age at the time of signing the informed consent form (ICF; ie, the study populations in the ESKETINTRD3001, ESKETINTRD3002, and ESKETINTRD3003 were < 65 years of age), a dose of 28 mg will be available. Based on PK data from ESKETINTRD1012 it is also possible that the 28 mg dose in the elderly may overlap with the 56 mg dose in younger patients, so addition of the 28 mg dose in the elderly may provide an efficacious dose while improving safety.

The use of flexible dosing for esketamine nasal spray may provide improved tolerability by gradually increasing to a higher dose and will also inform clinical practice, as many clinicians prefer to gradually increase, and then adjust as clinically required, the dose of antidepressant medication.

Optimization/Maintenance Phase

Subjects from the induction phase of 54135419TRD3008, who enter the optimization/maintenance phase will continue on the same dose of esketamine nasal spray from the induction phase and have a weekly intranasal treatment session frequency (ie, reduced frequency from the twice-weekly frequency in the induction phase).

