Subjects entering the optimization/maintenance phase from study ESKETINTRD3003 (Transferred Entry) will start at 56 mg. The dose may remain at 56 mg or be increased to 84 mg, as determined by the investigator based on efficacy and tolerability. In addition, subjects will have the option to have their current intranasal dosing frequency adjusted at the time of entry into 54135419TRD3008 study and should remain on the selected frequency from week 1 to week 4 (inclusive).

Subjects from the induction phase of ESKETINTRD3005 will have the intranasal treatment session frequency reduced to weekly. However, as the ESKETINTRD3005 study will be blinded at the time of entry into the current study, these subjects will start esketamine nasal spray with an initial dose of 28 mg (Week 1; Study Day 1) and have their dose adjusted over the following 3 weeks of the optimization/maintenance phase as described under the Section 6 Dosage and Administration.

Starting at Week 4, the frequency of intranasal treatment sessions will be individualized and subsequent intranasal treatment session frequency will be adjusted (if applicable) based on the algorithm below at fixed, 4-week intervals (starting at Week 4,) to once weekly, once every other week, or once every 4 weeks based on the severity of depression, as assessed by the CGI-S. This continued individualization of treatment session frequency is intended to allow subjects to sustain the antidepressant response while minimizing the frequency of intranasal treatment sessions required.

After Week 4 (ie, starting at Week 5), the dose can be adjusted based upon efficacy and tolerability, as determined by clinical judgment.

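### Subjects aged 65 or over who enter optimization/maintenance directly from 3001, 3002, 3006 or 3003 (Transferred Entry) have no written 28 mg starting dose, although the induction route gives that age group one (low priority)

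*Protocol*

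**What the plan says.** Section 6.1.2 of the protocol sets OP/MA dosing for Weeks 1 to 4 by the study the subject comes from. The Synopsis and the OP/MA part of Section 3.2.4 repeat the same rules.

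- Responders from 3001, 3002 or 3006: "subjects entering the optimization/maintenance phase should start at 56 mg. The dose may remain at 56 mg or be increased to 84 mg".
- 3006 subjects who did not meet response criteria: "subjects entering the optimization/maintenance phase from study ESKETINTRD3006 will start at 56 mg".
- 3003 Transferred Entry: "Subjects entering the optimization/maintenance phase from study ESKETINTRD3003 (Transferred Entry) will start at 56 mg".

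Each of these bullets names 56 or 84 mg only, and none mentions age. General dose adjustment is written from Week 5, when "the dose of esketamine for all subjects can be adjusted based upon efficacy and tolerability".

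The induction part of Section 3.2.4 does deal with age. It makes 28 mg available "for those subjects that become ≥ 65 years of age at the time of signing the informed consent form", with better tolerability as the aim, and adds that "it is also possible that the 28 mg dose in the elderly may overlap with the 56 mg dose in younger patients". Table 3 starts subjects aged 65 or over at 28 mg on Day 1; for Day 4 it says "The dose may remain at 28mg or be increased to 56mg".

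Within OP/MA, entrants from 3005 also begin low: "these subjects will start esketamine nasal spray with an initial dose of 28 mg (Week 1; Study Day 1").

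**The concern.** The protocol expects some subjects from 3001 to 3003 to have reached 65 by consent, and gives a tolerability reason for offering them 28 mg. It then writes that offer into one entry route only. No reason is stated for the difference. Blinding of the parent study explains why a 3001, 3002 or 3006 subject cannot simply continue a known dose, but not why age drops out of the rule.

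At stake is the first dose. Section 16.1 foresees entrants from 3001 and 3002 who responded to placebo plus an oral antidepressant. Such a subject, now 65 or over, could take a first ever esketamine dose of 56 mg, where the induction route would give 28 mg. Where the text says *will*, an investigator who prefers 28 mg has no written cover for it.

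**Working it through.** **Side by side, age 65 or over at consent**

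| Route | First dose | Doses named up to Week 4 | Source |
|---|---|---|---|
| Induction | 28 mg | 28, 56, 84 mg | Table 3 |
| OP/MA from 3001/3002/3006 | 56 mg | 56, 84 mg | Section 6.1.2 |
| OP/MA from 3003, Transferred Entry | 56 mg | 56, 84 mg | Section 6.1.2 |
| OP/MA from 3005 | 28 mg | 28, 56, 84 mg | Table 4 |

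Other 3003 and 3004 entrants to OP/MA have a one-time dose change at entry and are not part of this point.

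**Can one subject qualify for both routes?** Yes. Inclusion criterion 1.1 a.i (induction phase plus 2-week follow-up visit) does not exclude responders, and a.ii admits responders once 3003 is terminated. Section 9.1.4 lets 3006 non-responders enter at either phase, with sponsor approval.

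**First dose.** 56/28 = 2.0. Mean 40-minute levels in the Phase 2 study (Section 1.1.2.1) are 36.4, 58.1 and 72.5 ng/mL at 28, 56 and 84 mg, so 58.1/36.4 = 1.60. Assume that the elderly excess seen in study 1003 (17% for AUC, 21% for Cmax) also holds at 40 minutes:

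- 28 mg: 36.4 × 1.17 to 1.21 = 42.6 to 44.0 ng/mL
- 56 mg: 58.1 × 1.17 to 1.21 = 68.0 to 70.3 ng/mL

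The second range lies above the 58.1 measured at 56 mg and just below the 72.5 measured at 84 mg.

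**Next step.** 56 − 28 = 28 mg and 84 − 56 = 28 mg, so the increments are equal. In ratio the OP/MA step is smaller (84/56 = 1.5 against 56/28 = 2.0). It is also smaller in measured level: 72.5 − 58.1 = 14.4 against 58.1 − 36.4 = 21.7 ng/mL.

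**Blood pressure.** Mean (SD) peak systolic rises in Section 1.1.2.3 are 10.4 (10.44), 11.2 (15.01) and 17.1 (15.5) mm Hg. I assume the Period 1 group sizes of 11, 11 and 12.

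- 28 to 56 mg: difference 0.8; SE = √(10.44²/11 + 15.01²/11) = 5.51; Welch df 17.8; 95% CI −10.8 to 12.4
- 56 to 84 mg: difference 5.9; SE = √(15.01²/11 + 15.5²/12) = 6.36; df 20.9; 95% CI −7.3 to 19.1

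Neither difference is distinguishable from zero.

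**Maximum cumulative dose, with weekly OP/MA dosing**

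- Through Day 8: induction 28 + 56 + 84 = 168 mg; OP/MA 56 + 84 = 140 mg
- Over 4 weeks: induction 28 + 56 + 6 × 84 = 588 mg; OP/MA 56 + 3 × 84 = 308 mg; Table 4 route 28 + 56 + 84 + 84 = 252 mg

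The OP/MA route from 3001/3002/3006 or Transferred Entry therefore has a higher first dose but a lower ceiling than induction.

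**The case against.** The case for leaving the text alone has real weight.

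- **Few subjects.** Section 3.2.4 says 3001 to 3003 enrolled people under 65, so anyone affected from those studies turned 65 before consent. No count is given. The age range of 3006 is not stated. This stands.
- **The pharmacokinetic reason is indirect.** The overlap statement rests on study 1012, whose elderly group was 75 or over; the 3001 to 3003 subjects at issue have only recently turned 65. This weakens the reason, but the protocol itself applies it from 65.
- **Safeguards exist.** At 65 or over, Section 6.1 bars escalation unless the prior session's post-dose pressure was below 180/100, calls for repeat or postponement if predose pressure exceeds 150/90, and interrupts or stops dosing at set post-dose limits. Observation continues until the subject is ready for discharge. Some subjects can be entered at induction instead, and the responder bullet says *should*. These points reduce the risk, but none writes in a lower first dose.
- **Other texts might cover it.** SAP 1.2 speaks of dose adjustment in Weeks 1 to 4 but names no dose level or age rule. A footnote to the schematic in SAP Attachment 2 makes 28 mg an option at 65 or over, but the figure is not shown, so the phase it refers to cannot be seen.

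A reader might infer more than the documents support. A steeper later titration or greater total exposure is not shown; the arithmetic above says otherwise. The missing written step-down in Weeks 1 to 4 applies on these routes at every age, so it is not an age problem. The 28 mg start for 3005 is set by parent study and not by age at consent, so it is only a loose comparison. Nothing here shows that Transferred Entry subjects are esketamine-naive.

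**Conclusion.** The inconsistency holds and is confined to the starting dose. On the routes named, a subject aged 65 or over starts at 56 mg where induction would start at 28 mg, and where both routes are open the difference depends on point of entry alone. The first dose is doubled. The corresponding mean 40-minute level is about 1.6 times as high, on Phase 2 means not specific to older subjects. The documents do not show added harm: the systolic differences are too imprecise to support any claim, and the exposure ceiling is lower.

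This is a low-priority safety inconsistency. It rests on reading the 6.1.2 bullets as exhaustive for Weeks 1 to 4 and on at least one such subject having entered, which the documents neither confirm nor rule out. Timing lowers the priority further: participation ends by December 2022 at the latest, and the current SAP amendment is dated 14 February 2023, so a dosing edit would now have little or no practical effect.

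**What to change.** If entry is still open anywhere, add to the bullets concerned in the Synopsis, Section 3.2.4 and Section 6.1.2: *For subjects aged 65 or over at consent, 28 mg is permitted as the starting dose, with changes in 28 mg steps in Weeks 1-4.*

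The cost is one sentence per bullet. No new data are needed, and each device already holds 28 mg (Section 14.1.1). The downside is slower titration for a few subjects and a possibly shorter effect, since Section 1.1.2.2 reports that the 28 mg effect appears not to last as long. For that reason 28 mg is permitted and not forced.

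If entry has closed, the dosing edit has no effect. An optional descriptive addition is then to split the first-session dose-level table in SAP 4.3 by age (<65, 65 or over) and point of entry, so that the report shows who aged 65 or over started at 56 mg.

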7. TREATMENT COMPLIANCE

All doses of intranasal study drug will be self-administered by the subjects at the investigative site under the direct supervision of the investigator or designee and will be recorded.

The investigator or designated study-site personnel will maintain a log of all intranasal study drug dispensed and returned. Drug supplies for each subject will be inventoried and accounted for throughout the study (see Section 14.5 Drug Accountability).

8. PRESTUDY AND CONCOMITANT THERAPY

All study subjects should be taking a permitted oral antidepressant (per clinical judgment) throughout the duration of study participation. Changes to the oral antidepressant medication(s) that a subject is taking at study entry is permitted per clinical judgment of the investigator. If subject may benefit from an additional antidepressant medication (eg lithium, bupropion, adjunctive antipsychotic, etc.), the investigator should discuss with sponsor to determine whether continuing esketamine nasal spray still has a favorable benefit versus risk for the subject.

A list of prohibited medications is provided in [Attachment 1](#) as general guidance for the investigator (but is not all inclusive). The sponsor must be notified in advance (or as soon as possible thereafter) of any instances in which prohibited therapies are administered.

Concomitant therapies (including psychotherapy) must be recorded throughout the study beginning with signing of the informed consent and continuing up to the last visit. Information on concomitant therapies should also be obtained beyond this time only in conjunction with new or worsening adverse events until resolution of the event.

Subjects should continue to take their permitted concomitant medications (eg, antihypertensive medications) at their regular schedule; however, restrictions as outlined in Section 4.3 and Attachment 1 should be taken into account. Of note, if a subject has routinely taken his/her oral antihypertensive medications in the morning, the morning dose should be taken prior to esketamine nasal spray on intranasal dosing days.

There is no restriction regarding psychotherapy in this study and subjects may continue or start psychotherapy (including cognitive behavioral therapy; CBT) during the study.

All therapies (prescription or over-the-counter medications, including vaccines, vitamins, herbal supplements; non-pharmacologic therapies such as psychotherapy, acupuncture, and special diets) different from the study drug must be recorded in the CRF. Modification of an effective preexisting therapy should not be made for the explicit purpose of entering a subject into the study, unless permitted by protocol (eg, adjustment of blood pressure medications).

Rescue Medications

Rescue medications will not be supplied by the sponsor. In case of treatment-emergent adverse events that cannot be resolved by stopping further administration of esketamine nasal spray, the following rescue medications may be considered:

- For agitation or anxiety: As required, midazolam (maximum dose 2.5 mg orally or IM) or short acting benzodiazepine
- For nausea: As required, ondansetron 8 mg sublingually, metoclopramide (10 mg orally or IV or IM) or dimenhydrinate (25 to 50 mg, IV or IM)
- Unless clinically indicated, it is recommended that transient increases in blood pressure not be treated, as the blood pressure typically returns to predose values in 2 hours. The effect of any treatment may result in hypotension.

9. STUDY EVALUATIONS

9.1. Study Procedures

9.1.1. Overview

The Time and Events Schedules summarize the frequency and timing of safety, efficacy, and medical resource utilization measurements applicable to this study.

Visit-specific predose subject-reported outcomes assessments should be conducted/completed before any tests, procedures, or other consultations for that visit to prevent influencing subject perceptions.

A recommended order of study procedures will be provided to sites as a separate document.

Actual dates and times of assessments will be recorded in the source documentation and/or CRF.

The total blood volume to be drawn from each subject over the first 1 year period will be approximately 42 mL (Table 6) and will not exceed the amount of blood donated by a volunteer for a single charitable blood donation in 1 day (about 500 mL). The amount of blood volume collected during optimization/maintenance phase will be variable due to the nature of the study design. Repeat or unscheduled samples may be taken for safety reasons or for technical issues with the samples.

Additional serum or urine pregnancy tests may be performed, as determined necessary by the investigator or required by local regulation, to establish the absence of pregnancy at any time during the subject's participation in the study.

Table 6: Volume of Blood to be Collected from Each Subject

Phase Type of Sample	Volume per Sample(s), mL	Number of Samples per Subject	Total Volume of Blood (mL) ^a
Baseline Tests			
HbA1C (if applicable)	2	1	2
Hematology	2	1	2
Serum chemistry ^b	5	1	5
Induction Phase			
Hematology	2	1	2
Serum Chemistry	2.5	1	2.5
Optimization/Maintenance Phase			
HbA1C (if applicable)	2	3	6
Hematology	2	5 ^c	10 ^c
Serum Chemistry	2.5	5 ^c	12.5 ^c
Approximate volume of blood collected during the study^d			42 mL

^a Calculated as number of samples multiplied by amount of blood per sample.

^b Serum chemistry includes serum β -hCG pregnancy tests (for women of childbearing potential), and lipid panel.

^c The number of samples per subject (5) is representative of the samples collected that will be collected in the optimization/maintenance phase in an year. The length of the optimization/maintenance phase is variable and would decide the total number of samples collected during this phase and in turn the total volume of blood collected.

^d The approximate volume of blood (42 mL) collected during the study will vary as per the total volume of blood collected during the variable optimization/maintenance phase. The calculation shown is an estimate for a 1 year period.

Note: An indwelling IV cannula may be used for blood sample collection.

Note: Repeat or unscheduled samples may be taken for safety reasons or technical issues with the samples.

